### Spelling Format

English US (or English UK).

### Presentation of Treatment Groups

All summaries will be presented by assigned dose level. Dose expansion stage patients will be included in their dose level group and presented together with dose escalation patients receiving the same dose level.

### Listings

All listings will be ordered by the following (unless otherwise indicated in the template):

- Treatment group (ascending dose level in Stage 1, and Stage 2: CLL/SLL, FL, MZL, LPL/WM, MCL, PTCL, and CBCL)
- Patient ID,
- Visit (where applicable)
- Date (where applicable),

For listings where screen failed patients are included, these will appear in a category after the other treatment groups labeled 'Screen Failed'.

HMPL-523

---

## APPENDIX 4. INTERNATIONAL WORKSHOP ON CHRONIC LYMPHOCYTIC LEUKEMIA (IWCLL) UPDATE OF THE NATIONAL CANCER INSTITUTE-WORKING GROUP (NCI-WG) GUIDELINES: RESPONSE CRITERIA

### Complete Response (CR)

CR requires all of the following criteria as assessed no earlier than 2 months after completion of therapy:

- Peripheral blood lymphocytes (evaluated by blood and differential count) below  $4 \times 10^9/L$  (4,000/ $\mu$ L)
- Absence of significant lymphadenopathy (nodes  $\leq 15$  mm in longest diameter or any extra nodal disease) by physical examination and CT scan.
- No hepatomegaly or splenomegaly by physical examination or CT scan, as appropriate.
- Absence of disease or constitutional symptoms (B symptoms).
- Blood counts above the following values:
  - Neutrophils  $> 1.5 \times 10^9/L$  [1500/ $\mu$ L] (without growth factors)
  - Platelets  $> 100 \times 10^9/L$  [100,000/ $\mu$ L] (without platelet transfusion or growth factors)
  - Hemoglobin  $> 110$  g/L [11 g/dL] (without blood transfusions or erythropoietin)
- Bone marrow aspirate and biopsy should be performed 3 months after last treatment when clinical and laboratory results listed above demonstrate a CR/cytopenic CR has been achieved. Bone marrow at least normocellular for age,  $< 30\%$  of nucleated cells being lymphocytes. Lymphoid nodules should be absent. If the bone marrow is hypocellular, a repeat determination should be made in 4 weeks or when peripheral blood counts have recovered. However, this time interval should not exceed 6 months. A marrow biopsy should be compared to a pre-treatment marrow if available.

In patients who are otherwise in a complete remission, but bone marrow nodules can be identified histologically, immunohistochemistry should be performed to define whether these nodules are composed of primarily T cells or lymphocytes other than CLL cells, or CLL cells. Patients with residual CLL cells should be considered to be PR (nPR).

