APPENDIX 3 PK AND PHARMACODYNAMICS SAMPLING TIME POINTS (DOSE EXPANSION STAGE)^e

Visit Cycle and Day ^f	Time Point ^d	PK Sample	Pharmacodynamics Sample
Cycle 1 Day 1	Pre-dose ^a	X	X
	30 minutes (±5 minutes) post-dose	X	-
	1 hour (±5 minutes) post-dose	X	-
	2 hours (±10 minutes) post-dose	X	-
	4 hours (±15 minutes) post-dose	X	-
	6 hours (±15 minutes) post-dose	X	-
	8 hours (±15 minutes) post-dose	X	-
Cycle 1 Day 2	Pre-dose ^a	X	-
Cycle 1 Day 28 ^{b, g}	Pre-dose ^a	X	-
	30 minutes (±5 minutes) post-dose	X	-
	1 hour (±5 minutes) post-dose	X	-
	2 hours (±10 minutes) post-dose	X	-
	4 hours (±15 minutes) post-dose	X	-
	6 hours (±15 minutes) post-dose	X	-
	8 hours (±15 minutes) post-dose	X	-
Cycle 2 Day 1 ^c	Pre-dose ^a	X	X
Cycle 3 Day 1	Pre-dose ^a	X	X
Cycle 5 Day 1 and every other cycle thereafter ^h	NA	-	

eCRF = electronic case report form; NA = not applicable; PK = pharmacokinetic.

- ^a The blood samples will optimally be obtained within 5 minutes prior to dosing but may be obtained up to 30 minutes prior to dosing.
- ^b Cycle 1 Day 28 shares the window with Cycle 2 Day 1, which is ±3 days and should be immediately followed by Cycle 2 Day 1.
- ^c Cycle 2 Day 1 pre-dose is the 24-hour (+15 mins) PK sample of Cycle 1 Day 28.
- ^d The actual date and time of the PK samples must be recorded in the eCRF.
- ^e Blood samples that remain after PK analysis of HMPL-523 may be used exclusively for exploratory biomarker purposes.
- ^f On PK sampling day, study drug must be taken at the investigative site under the supervision of the investigator or designee and should not be taken at home on the morning of the visits. The date and time of the dose administered on the day of PK collection and 1 day before PK collection must be recorded in the eCRF.
- ^g In case PK samples planned for Cycle 1 Day 28 does not occur due to whatever reasons, they may be rescheduled for collection in subsequent cycles. Please consult the sponsor for further guidance and instructions.
- ^h Upon implementation of Protocol Amendment 5, PK samples for measurement of plasma concentrations of HMPL-523 will not be collected on Cycle 5 Day 1 and beyond.

APPENDIX 4 INTERNATIONAL WORKSHOP ON CHRONIC LYMPHOCYTIC LEUKEMIA UPDATE OF THE NATIONAL CANCER INSTITUTE-WORKING GROUP GUIDELINES: RESPONSE CRITERIA

Complete Response (CR)

Complete response requires all of the following criteria as assessed no earlier than 2 months^a after completion of therapy:

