- Peripheral blood lymphocytes (evaluated by blood and differential count) below $4 \times 10^9/L$ (4000/ μ L)
- Absence of significant lymphadenopathy (nodes ≤ 15 mm in longest diameter or any extra nodal disease) by physical examination and computed tomography (CT) scan
- No hepatomegaly or splenomegaly by physical examination or CT scan, as appropriate
- Absence of disease or constitutional symptoms (B symptoms).
- Blood counts above the following values:
 - Neutrophils $> 1.5 \times 10^9/L$ (1500/ μ L) (without growth factors)
 - Platelets $> 100 \times 10^9/L$ (100000/ μ L) (without platelet transfusion or growth factors)
 - Hemoglobin > 110 g/L (11 g/dL) (without blood transfusions or erythropoietin)
- Bone marrow aspirate and biopsy should be performed 3 months after the last treatment when the clinical and laboratory results listed above demonstrate a CR/cytopenic CR has been achieved. Bone marrow should be at least normocellular for age, with $< 30\%$ of nucleated cells being lymphocytes. Lymphoid nodules should be absent. If the bone marrow is hypocellular, a repeat determination should be made in 4 weeks or when peripheral blood counts have recovered. However, this time interval should not exceed 6 months. A marrow biopsy should be compared to a pretreatment marrow if available.

In patients who are otherwise in a complete remission but bone marrow nodules can be identified histologically, immunohistochemistry should be performed to define whether these nodules are composed primarily of T cells or lymphocytes other than chronic lymphocytic leukemia (CLL) cells, or CLL cells. Patients with residual CLL cells should be considered to be partial response (PR) (nodular partial response [nPR]).

Complete Response with Incomplete Bone Marrow Recovery

Patients who fulfill the criteria for CR (including bone marrow) but who have persistent cytopenia, anemia, thrombocytopenia, or neutropenia. The marrow evaluation described above should be performed with scrutiny and not show any clonal infiltrate.

Partial Response (PR)

To be considered PR, patients must exhibit the following features for at least 2 months from end of treatment:

- $\geq 50\%$ decrease in peripheral blood lymphocyte count from the pre-treatment value

AND either a

^a Bone marrow biopsies should be performed at least 2 months after the last treatment and if clinical and laboratory results demonstrate that a CR has been achieved.

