#### Best overall response (BOR)

The best overall response (BOR) for an individual patient is the best response recorded from the start of treatment until progression or the date of any further anticancer therapy, whichever comes first.

Best overall response is determined from the sequence of responses assessed as below:

- For CLL guideline: Complete Response (CR), CR with incomplete bone marrow recovery (CRi), Partial Response (PR), Nodular Partial Response (nPR), Partial Response with Lymphocytosis (PR-L), Stable Disease (SD), Progressive Disease (PD), Not all evaluated (NE).
- For WM guideline: Complete Response (CR), Very Good Partial Response (VGPR), Partial Response (PR), Minor Response (MR), Stable Disease (SD), Progressive Disease (PD), Not Evaluated (NE).
- For Other Lymphomas guideline: Complete Response (CR), Partial Response (PR), Stable Disease (SD), Progressive Disease (PD), Not Evaluated (NE).

For patients with multiple assessment for same visit, the earliest date will be selected for PD, while the latest date will be selected for other response.

Patients with BOR "NE" will be summarized by reason for having NE status. The following reasons will be used:

- No valid post-baseline assessment
- All post-baseline assessments have overall response NE

Patients with a BOR of "Unknown" or "NE" will be considered non-responders in estimating response rates.

HMPL-523

The number and percentage of patients with BOR of CR, CRi, VGPR, PR, nPR, MR, PR-L, SD, PD, and NE will be summarized by dose level and overall in Stage 1, by the malignancy type and overall in Stage 2.

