### Partial Response (PR)

HMPL-523

To be considered PR patients must exhibit the following features for at least 2 months from end of treatment:

- $\geq 50\%$  decrease in peripheral blood lymphocyte count from the pre-treatment value
  - AND either a
  - $\geq 50\%$  reduction in lymphadenopathy (sum of longest diameter of the 6 largest lymph nodes by physical exam and 50% reduction in the sum of product of diameter (SPD) of the 6 largest lymph nodes measured by CT scan). No increase in any node and no new enlarged lymph node. In small lymph nodes (< 2 cm in diameter), an increase of less than 25% is not considered to be significant.
  - OR
  - $\geq 50\%$  reduction of liver enlargement if enlarged at baseline as assessed by CT scan
  - OR
  - $\geq 50\%$  reduction of spleen enlargement if enlarged at baseline as assessed by CT scan
- Plus at least one of the following:
  - Neutrophils  $> 1.5 \times 10^9/L$  [1500/ $\mu L$ ] (without growth factors) or  $\geq 50\%$  increase of pre-treatment value
  - Platelets  $> 100 \times 10^9/L$  [100,000/ $\mu L$ ] (without platelet transfusion growth factors) or  $\geq 50\%$  increase of pre-treatment value
  - Hemoglobin  $> 110$  g/L [11 g/dL] (without blood transfusions or erythropoietin) or  $\geq 50\%$  increase of pre-treatment value

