#### **Partial Response with Lymphocytosis (PR-L)**

Patients achieved partial response with CLL-related signs or symptoms other than lymphocytosis will be considered PR-L and continue on therapy until the occurrence of definitive disease progression other than lymphocytosis alone.

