#### **Stable Disease (SD)**

Patients who have not achieved a CR or a PR, or who have not exhibited PD, will be considered to have stable disease

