#### **Overall Response Rate (ORR)**

Response is classified into classical-ORR, defined as the proportion of patients with CR, complete response with incomplete marrow recovery (CRi), nodular partial response (nPR), or partial response (PR), as determined by the investigator; and neo-ORR defined as the proportion of patients with CR, complete response with incomplete marrow recovery (CRi), nodular partial response (nPR), partial response with lymphocytosis (PR-L) or partial response (PR), as determined by the investigator.

Adapted from:

Hallek M. et al. Guidelines for the diagnosis and treatment of chronic lymphocytic leukemia *Blood*. 2008 Jun 15;111(12):5446-56.

Cheson B. et al. Novel targeted agents and the need to refine clinical end points in chronic lymphocytic leukemia. *Journal of Clinical Oncology*, 2012 Vol 30, No 23, 2820-2822.

a Bone marrow biopsies should be performed at least 3 months after completion of therapy.

HMPL-523

**APPENDIX 5. CONSENSUS-BASED UNIFORM RESPONSE CRITERIA  
FOR WM DEVELOPED BY THE IWWM, UPDATED IN  
THE SIXTH IWWM**

Response category	Description
Complete Response (CR)	Absence of serum monoclonal IgM protein by immunofixation Normal serum IgM level Complete resolution of extramedullary disease, ie, lymphadenopathy and splenomegaly if present at baseline Morphologically normal bone marrow aspirate and trephine biopsy
Very Good Partial Response (VGPR)	Monoclonal IgM protein is detectable ≥90% reduction in serum IgM level from baseline a Complete resolution of extramedullary disease, ie, lymphadenopathy/splenomegaly if present at baseline No new signs or symptoms of active disease
Partial Response (PR)	Monoclonal IgM protein is detectable ≥50% but <90% reduction in serum IgM level from baseline a Reduction in extramedullary disease, ie, lymphadenopathy/splenomegaly if present at baseline No new signs or symptoms of active disease
Minor Response (MR)	Monoclonal IgM protein is detectable ≥25% but <50% reduction in serum IgM level from baseline a No new signs or symptoms of active disease
Stable Disease (SD)	Monoclonal IgM protein is detectable <25% reduction and <25% increase in serum IgM level from baseline a No progression in extramedullary disease, ie, lymphadenopathy/splenomegaly No new signs or symptoms of active disease

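### Appendix 4 dates CLL CR and PR from the end of therapy, but dosing runs to progression and the response endpoints run from the start of treatment

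*SAP*

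**What the plan says.** **Criteria.** SAP Appendix 4 says "CR requires all of the following criteria as assessed no earlier than 2 months after completion of therapy". For PR it says "To be considered PR patients must exhibit the following features for at least 2 months from end of treatment". Protocol Appendix 4 matches: "Complete response requires all of the following criteria as assessed no earlier than 2 months" after therapy is completed for CR, and for PR "patients must exhibit the following features for at least 2 months from end of treatment". CRi requires the CR criteria, and nPR describes a patient otherwise in complete remission, so both inherit the CR timing. The remaining default is: "Patients who have not achieved a CR or a PR, or who have not exhibited PD, will be considered to have stable disease".

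**PR-L.** The same appendix says "Patients achieved partial response with CLL-related signs or symptoms other than lymphocytosis will be considered PR-L and continue on therapy".

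**Dosing.** Protocol 4.5 gives HMPL-523 in repeated 28-day cycles until progression or another stopping reason. Protocol 5.7.3 makes progression a mandatory reason to stop.

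**Endpoints.** SAP 16.1.1 defines BOR as "the best response recorded from the start of treatment until progression or the date of any further anticancer therapy, whichever comes first". TTR runs from first dose to first response. Classical ORR for CLL counts CR, CRi, nPR and PR; neo-ORR adds PR-L. Appendix 4 leaves the call to the investigator: CR, CRi, "nodular partial response (nPR), or partial response (PR), as determined by the investigator". The Protocol synopsis and 5.6.12 schedule tumor assessments every 8 weeks for 24 weeks, then every 12 weeks.

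**The concern.** The post-therapy timing suits a treatment course that is completed and then assessed. This study has no such completion: a patient who does well stays on drug until progression, and at progression the BOR window closes. There is then no 2-month off-drug period in which CR or PR could be met.

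No passage adapts the rule. The protocol's modified IWCLL 2008 reference points back to Appendix 4 without saying that the timing is what was modified. Appendix 4 separates during-treatment from after-treatment assessment for progression, but not for CR or PR. PR-L is written for patients who stay on therapy. Either it inherits the PR timing, or the appendix accepts an on-treatment partial response in one place and excludes it in another.

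Stage 2 efficacy is a primary objective. The same scans can therefore give two CLL response rates, and a reader could not tell which rule was used.

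**Working it through.** The plan states no figure for this point. The check sets the rules side by side and then sizes the affected group.

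**1. Literal reading.** For a patient dosed to progression, last dose and progression roughly coincide, so time off drug before BOR closes is about 0, against 2 × 30.4375 = 60.9 days required. CR, CRi, nPR and PR are unattainable and the patient defaults to SD. Classical ORR, CR rate, DoR and TTR lose that patient. The clinical benefit rate does not, because it counts SD.

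**2. The off-drug route.** A patient who stops without progression or new therapy can still qualify.
- The end-of-treatment visit falls at most 30 + 7 = 37 days after last dose, which is too early.
- The first scheduled scan that qualifies is the first quarterly visit, about day 91 off drug (assuming a quarter is 91.3 days).
- Tumor follow-up ends 12 months after first dose, so the patient must stop by about 365.25 − 91.3 = day 274 (267 to 281 with the ±7-day window). An unscheduled scan would extend this to about month 12 − 2 = 10.

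**3. TTR under the literal rule.** With one day of dosing and then 2 months off drug, the SAP formula gives (60.875 + 1)/30.4375 = 2.03 months as a minimum. The first scheduled scan falls at day 49 to 63, which is 1.61 to 2.07 months. The China study (Protocol 2.2.4.4, Cohort A) reports a median CLL/SLL TTR of 1.9 months, or 1.9 × 30.4375 = 58 days. That is below the minimum and fits on-treatment scoring, if its criteria were the same, which the documents do not say.

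**4. Scope.** Protocol Table 2 lists 1 CLL + 7 post-BTK CLL = 8 of 48. This is an upper bound: SAP 16.1.1 scores SLL by Lugano, and ORR uses the Response Evaluable Set, whose CLL count is not given. Stage 1 CLL patients add an unstated number.

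**5. Responders at stake (illustration; assumes the China rates carry over).**
- CLL only: 12 evaluable patients, ORR 50.0% (21.1 to 78.9), so 6/12. The Clopper-Pearson interval reproduces.
- Prior BTK exposure: ORR 50% in 8 CLL/SLL patients (Protocol 2.2.4.5), the closest match because 7 of the 8 here are post-BTK.
- Both give 8 × 0.50 = 4 patients.
- The cohort's ORR includes PR-L: 1 CR + 4 PR + 4 PR-L = 9/16 = 56.3%. No CLL-only split is given, but totals bound it. SLL had 75% of 4 = 3 responders and CLL 6. With 4 PR-L overall, CLL had between 2 and 5 CR/PR of 12. Scaled to 8 patients, that is 1.3 to 3.3.

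**6. Effect on the estimate (Clopper-Pearson 95%, n = 8).**

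| Counted as responders | Rate | 95% CI |
|---|---|---|
| 4 (on-treatment, PR-L included) | 50% | 15.7 to 84.3 |
| 2 (qualify off drug) | 25% | 3.2 to 65.1 |
| 1 (qualifies off drug) | 12.5% | 0.3 to 52.7 |
| 0 | 0% | 0 to 36.9 |

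Each reclassified patient moves a pooled rate by 1/8 = 12.5 points.

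**The case against.** The strongest reply is that nobody would score this trial literally. Investigators assess every 8 weeks from the start, BOR takes responses recorded from start of treatment, TTR runs from first dose, and Protocol 5.6.13 asks for marrow confirmation when CR looks likely without requiring the patient to be off drug. On-treatment scoring is therefore the likelier practice, and the SAP would then count those responses. This stands as a judgment of likelihood. It does not reconcile the text: the rates would then rest on a rule that the documents do not state, and sites could differ.

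Size is also a fair objection. The groups are of 1 and 7 patients, enrollment is closed, efficacy is descriptive, and no power calculation or decision threshold depends on the result. That stands and limits the weight of the point.

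Two stronger readings are tempting.
- A reader might infer that CLL ORR will be reported as zero. The documents do not support that: it needs every investigator to withhold on-treatment responses and no patient to qualify off drug.
- A reader might infer that open-ended follow-up gives ample room for off-drug responses, because Protocol 4.1 and SAP 4.1 describe follow-up without a time limit. Those are general descriptions. The 12-month limit stands in all the specific tumor follow-up rules: the synopsis, Protocol 5.6.12 and 5.7.1, and Appendix 1 footnote 3 in both documents.

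**Conclusion.** The inconsistency is real and present in both documents. Appendix 4 applied literally turns on-treatment CLL responses into stable disease. Applied as investigators more likely work, it leaves classical ORR, CR rate, DoR and TTR departing from the written criteria. The PR-L wording conflicts with the PR timing under either practice.

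The documents do not show which practice was followed. About 4 of 8 patients at stake, PR-L included, rests on all 8 having CLL, all being in the Response Evaluable Set, and the China rates carrying over. The number is smaller if any of these fails, or if PR-L is accepted as an on-treatment category. The point deserves correction before lock because the affected rates belong to a primary objective, but it does not threaten the trial's design.

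**What to change.** SAP Section 2 allows revision before final database lock.

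1. In SAP 16.1.1, and in Appendix 4 if it is amended, state that because treatment is continuous the CLL categories CR, CRi, nPR, PR and PR-L are judged at any valid tumor assessment, scheduled or unscheduled, from start of treatment within the BOR window, in place of the end-of-therapy timing.
2. State whether PR's 2-month persistence is kept, counted from the first on-treatment observation, or dropped. If it is dropped, show CLL ORR both ways. Replacing the timing without saying this would silently let a single unconfirmed observation count.
3. Check recorded CLL responses against the rule. If persistence is kept, a recorded PR may be reclassified.
4. Record in the CSR that the rule was set after the data snapshot that supported a publication (SAP Section 5).

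Separately, the marrow-timing passages must be reconciled with one another: Protocol 5.6.13 (when CR is likely), Appendix 1 footnote 17 (end of therapy), the Appendix 4 body text (3 months after last treatment), and the Appendix 4 footnotes (at least 2 months in the Protocol, at least 3 in the SAP). I do not propose which is right.

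Cost: a few sentences, a check of at most 8 Stage 2 records plus any Stage 1 CLL patients, and possibly one extra table. No new data are needed.

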### CR with incomplete bone marrow recovery (CRi)

Patients who fulfill the criteria for CR (including bone marrow) but who have persistent cytopenia; anemia, thrombocytopenia or neutropenia. The bone marrow evaluation described above should be performed with scrutiny and not show any clonal infiltrate.

### Partial Response (PR)

HMPL-523

To be considered PR patients must exhibit the following features for at least 2 months from end of treatment:

- $\geq 50\%$  decrease in peripheral blood lymphocyte count from the pre-treatment value
  - AND either a
  - $\geq 50\%$  reduction in lymphadenopathy (sum of longest diameter of the 6 largest lymph nodes by physical exam and 50% reduction in the sum of product of diameter (SPD) of the 6 largest lymph nodes measured by CT scan). No increase in any node and no new enlarged lymph node. In small lymph nodes (< 2 cm in diameter), an increase of less than 25% is not considered to be significant.
  - OR
  - $\geq 50\%$  reduction of liver enlargement if enlarged at baseline as assessed by CT scan
  - OR
  - $\geq 50\%$  reduction of spleen enlargement if enlarged at baseline as assessed by CT scan
- Plus at least one of the following:
  - Neutrophils  $> 1.5 \times 10^9/L$  [1500/ $\mu L$ ] (without growth factors) or  $\geq 50\%$  increase of pre-treatment value
  - Platelets  $> 100 \times 10^9/L$  [100,000/ $\mu L$ ] (without platelet transfusion growth factors) or  $\geq 50\%$  increase of pre-treatment value
  - Hemoglobin  $> 110$  g/L [11 g/dL] (without blood transfusions or erythropoietin) or  $\geq 50\%$  increase of pre-treatment value

